6.3.2. Analysis Methods for Secondary Efficacy Variables

The analysis of the secondary efficacy variables will be performed on the ITT analysis set without retrieved dropout data.

6.3.2.1. Change from Baseline in the Weekly Average of Daily Trough Morning (Predose and Prerescue Bronchodilator) Peak Expiratory Flow (PEF) Over the 12-week Treatment Period

The analysis of change from baseline in the weekly average of daily morning (predose and pre-rescue bronchodilator) PEF over the 12-week treatment period will be performed using an MMRM with effects due to baseline weekly average of daily morning PEF, sex, age, (pooled) investigational center, previous therapy (ICS or NCS), week, treatment, and week-by-treatment interaction. No explicit structure will be assumed for the covariance among the repeated measures. However, if there is a convergence problem with unstructured covariance, then a compound symmetry covariance structure will be assumed.

6.3.2.2. Change from Baseline in the Weekly Average of Total Daily (24-hour) use of Albuterol/Salbutamol Inhalation Aerosol (Number of Inhalations) Over Weeks 1 Through 12

The change from baseline in the weekly average of total daily (24-hour) use of albuterol/salbutamol inhalation aerosol (number of inhalations) over weeks 1 through 12 will be analyzed using an MMRM with effects due to baseline value, sex, age, (pooled) investigational center, previous therapy (ICS or NCS), week, treatment, and week-by-treatment interaction. No explicit structure will be assumed for the covariance among the repeated measures. However, if there is a convergence problem with unstructured covariance, then a compound symmetry covariance structure will be assumed.

6.3.2.3. **Change from Baseline in the Weekly Average of the Total Daily Asthma Symptom Score (Defined as the Average of the Daytime and Nighttime Scores) Over Weeks 1 Through 12**

The change from baseline in the weekly average of the total daily asthma symptom scores over weeks 1 through 12 will be analyzed using an MMRM with effects due to baseline score, sex, age, (pooled) investigational center, previous therapy (ICS or NCS), week, treatment, and week-by-treatment interaction. No explicit structure will be assumed for the covariance among the repeated measures. However, if there is a convergence problem with unstructured covariance, then a compound symmetry covariance structure will be assumed.

6.3.2.4. **Change from Baseline in Asthma Control (Measured by Childhood Asthma Control Test [C-ACT] Score Over the 12-week Treatment Period**

The change from baseline in C-ACT score over the 12-week treatment period will be analyzed using an MMRM with effects due to baseline C-ACT score, sex, age, (pooled) investigational center, previous therapy (ICS or NCS), week, treatment, and week-by-treatment interaction. No explicit structure will be assumed for the covariance among the repeated measures. However, if there is a convergence program with unstructured covariance, then a compound symmetry covariance structure will be assumed.

6.3.2.5. **Time to First Onset of Effect in Daily Rescue Medication Use**

The time to first onset of effect, defined as the number of days elapsed from the date of randomization to the first date of decrease from baseline in daily rescue medication use. Patients who first have a decrease of effect will be counted as an event in the analysis; otherwise, patients will be right-censored at the date of last IMPDV assessments.

The analysis of time to first onset of effect will be performed using a log-rank test to compare the survival curves. Time to first onset of effect will be displayed graphically with a Kaplan-Meier figure, and median time to first onset of effect and associated 95% CIs will be provided.

Example SAS code for this analysis:

```
proc lifetest data=toasm method=KM outsurv=yyy;
  where treat in ("A", "D");
  time aval*cnsr(0);
  strata treat;
  ods output CensoredSummary=count
             Quartiles=qrt
             productlimitestimates=k mest
             HomTests = pvals(where=(upcase(test) = "LOG-RANK"));
run;
where: aval is days from the date of first double-blind study IMP
to the date of event or censoring. CNSR is the censoring flag (0=no
event [censored]; 1=event [meet criteria]). The code is executed for
each pair of treatment comparisons of interest.
```

6.3.2.6. Proportion of Patients Discontinued From IMP for Asthma Exacerbation During the 12-week Treatment Period

The proportion of patients discontinued from IMP for asthma exacerbation during the 12-week treatment period will be analyzed using a logistic regression model with effects due to previous therapy (ICS or NCS) and treatment. In case the algorithm does not converge, a stratified (based on previous therapy [ICS or NCS]) Cochran-Mantel-Haenszel (CMH) test will be used to analyze the proportion of patients discontinued from IMP for asthma exacerbation during the 12-week treatment period.

Example SAS code for this analysis:

```
proc logistic data=proasm descending;
    class treat therapy;
    model flag = treat therapy;
    output out=yyy predicted=pp;
    ods output    oddsratios=oddsratios
                parameterestimates=parameterestimates
                contrastTest=contrast
                convergencestatus=convergencestatus;
run;
where: flag is either 1 (event) or 0 (no event)
```

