6.4.2. Analysis Methods for Other Efficacy Variables

The analysis of the other efficacy variables will be performed on the ITT analysis set without retrieved dropout data.

6.4.2.1. Change from Baseline in the Weekly Average of the Total Daily (24-hour) use of Albuterol/Salbutamol Inhalation Aerosol (Number of Inhalations) at Weeks 4, 8, and 12

The change from baseline in weekly average of total daily (24-hour) use of albuterol/salbutamol inhalation aerosol (number of inhalations) at weeks 4, 8, and 12 will be analyzed using an MMRM with effects due to baseline value, sex, age, (pooled) investigational center, previous therapy (ICS or NCS), week, treatment, and week-by-treatment interaction. No explicit structure will be assumed for the covariance among the repeated measures. However, if there is a convergence problem with unstructured covariance, then a compound symmetry covariance structure will be assumed.

6.4.2.2. Change from Baseline in the Percentage of Rescue-free Days (Defined as 24-hour Periods with no Rescue Medication Usage) During the 12-week Treatment Period

The change from baseline in the percentage of rescue-free days (defined as 24-hour periods with no use of rescue medication recorded in the morning and evening) as recorded in the patient diaries during the 12-week treatment period will be summarized and compared between treatment groups using the Wilcoxon-Mann-Whitney test.

Example SAS code for this analysis:

```
proc npar1way data=salf wilcoxon;
  where treat in ("A", "D");
  class treat;
  var change;
  output out=yyy wilcoxon; run;
```

where: change is the change from baseline in percentage of rescue-free days. The code is executed for each pair of treatment comparisons of interest.

6.4.2.3. Change from Baseline in the Percentage of Symptom-free Days (Defined as 24-hour Periods with Asthma Symptom Score of 0) During the 12-week Treatment Period

The change from baseline in the percentage of symptom-free days (defined as 24-hour periods with asthma symptom scores of zero) as recorded in the patient diaries during the 12-week treatment period will be summarized and will be compared between treatment groups using the Wilcoxon-Mann-Whitney test.

6.4.2.4. Change from Baseline in the Percentage of Asthma-control Days (Defined as 24-hour Periods with Asthma Symptom Score of 0 and no Rescue Medication usage) During the 12-week Treatment Period

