7.2. Multiple Comparisons for the Secondary Analysis

If the p-value is less than 0.05 for the 3 inferential comparisons in the primary analysis, inferential testing will be extended to the secondary analysis.

Testing of secondary efficacy variables for the study drugs will be performed in the sequential manner described in [Table 8](#) (Fp MDPI) and [Table 9](#) (FS MDPI).

Treatment comparisons will begin with the change from baseline in weekly average of daily trough morning PEF (first secondary endpoint) with Fp MDPI 50 mcg versus placebo for

Fp MDPI, or FS MDPI 50/12.5 mcg versus placebo for FS MDPI. If the resulting p-value is less than 0.05, the next comparison(s) of interest will be made according to the direction of the arrows. To the right, this will be the same endpoint to compare Fp MDPI 25 mcg versus placebo (Fp MDPI), or FS MDPI 50/12.5 mcg versus Fp MDPI 25 mcg (FS MDPI). To the next endpoint, this will be the change from baseline in the weekly average of the total daily (24-hour) use of albuterol/salbutamol inhalation aerosol (second secondary endpoint) at the Fp MDPI 50 mcg versus placebo (Fp MDPI), or FS MDPI 50/12.5 mcg versus placebo (FS MDPI).

This process will continue testing sequentially through the next study drug/strength for each variable and at a given strength through the order presented in [Table 8](#) and [Table 9](#) until either all comparisons of interest are made, or until the point at which the resulting p-value for a comparison is greater than 0.05. At the point where the p-value is greater than 0.05, no further comparisons of either that strength or that measure can be made. This procedure allows for control of the Type I error for comparisons at a particular study drug/strength over the 6 secondary endpoints, as well as comparisons over study drugs/strengths within a particular endpoint. However, it does not control the overall Type I error, nominal p-value will be reported.

No multiplicity adjustment will be made for other efficacy analyses.

Table 8: Sequence of Testing Secondary Endpoints for Fp MDPI

Secondary Endpoint	Hypothesis Testing	
	Fp MDPI 50 mcg vs. Placebo	Fp MDPI 25 mcg vs. Placebo
[A] Change from baseline in weekly average of daily trough morning PEF over the 12-week treatment period	↓ →	↓
[B] Change from baseline in the weekly average of total daily (24-hour) use of albuterol /salbutamol inhalation aerosol (number of inhalations) over weeks 1 through 12	↓ →	↓

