mnar adjust( wk5 / shift=&sj adjustobs=(trt='B' ) );
mnar adjust( wk6 / shift=&sj adjustobs=(trt='B' ) );
mnar adjust( wk7 / shift=&sj adjustobs=(trt='B' ) );
mnar adjust( wk8 / shift=&sj adjustobs=(trt='B' ) );
mnar adjust( wk9 / shift=&sj adjustobs=(trt='B' ) );
mnar adjust( wk10 / shift=&sj adjustobs=(trt='B' ) );
mnar adjust( wk11 / shift=&sj adjustobs=(trt='B' ) );
mnar adjust( wk12 / shift=&sj adjustobs=(trt='B' ) );

mnar adjust( wk1 / shift=&sj adjustobs=(trt='C' ) );
mnar adjust( wk2 / shift=&sj adjustobs=(trt='C' ) );
mnar adjust( wk3 / shift=&sj adjustobs=(trt='C' ) );
mnar adjust( wk4 / shift=&sj adjustobs=(trt='C' ) );
mnar adjust( wk5 / shift=&sj adjustobs=(trt='C' ) );
mnar adjust( wk6 / shift=&sj adjustobs=(trt='C' ) );
mnar adjust( wk7 / shift=&sj adjustobs=(trt='C' ) );
mnar adjust( wk8 / shift=&sj adjustobs=(trt='C' ) );
mnar adjust( wk9 / shift=&sj adjustobs=(trt='C' ) );
mnar adjust( wk10 / shift=&sj adjustobs=(trt='C' ) );
mnar adjust( wk11 / shift=&sj adjustobs=(trt='C' ) );
mnar adjust( wk12 / shift=&sj adjustobs=(trt='C' ) );
```

```
var trt &covlist wk1 - wk12;
```

```
run;
```

where: the order of &covlist includes: sex, (pool) investigational center, previous therapy, base, and age

Note: wk1 - wk12 is the AVAL raw data, change from baseline values should not be used in PROC MI procedure.

The same shift will be assumed for all weekly average and all active treatments.

2. The MMRM model will be fitted to the completed datasets using the model that was used for analysis. The difference will be estimated in adjusted LS means and p-value. SAS code similar to the following will be used:

```
ods output diffs=midiffs;
proc mixed data=dateset;
  by shift;
  class usubjid sex center therapy visit trt;
  model chg=base sex age center therapy visit trt visit*trt /
    ddfm=KR alpha=0.05;
  repeated visit / type=un sub=usubjid(trt) r;
    ** repeated visit / type=cs sub=usubjid(trt) r;
    ** if type=un fails to converge;
  lsmeans trt / diff cl;
run;
```

3. The results from the MMRM models will be combined using the following code:

```
data diffdt;
  set midiffs;
  comparison=trt||' vs '||left(_trt);
run;
proc sort data=diffdt;
  by comparison shift;
run;
ods output parameterestimates=miparm1;
proc mianalyze data=diffdt alpha=0.05 theta0=0;
  by comparison shift;
  modeleffects estimate;
  stderr stderr;
run;
```

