APPENDIX E. SENSITIVITY ANALYSIS: MMRM

Similar to the primary estimand, retrieved dropout data will not be used in this sensitivity analysis. Missing data are not implicitly imputed in the MMRM analysis; however, all nonmissing data for a patient will be used within the analysis to estimate the time-averaged difference between treatment groups over 12 weeks. This analysis represents a MAR assumption.

Change from Baseline in Weekly Average of the Percent Predicted Trough Morning FEV₁ Over Week 12:

The sensitivity analysis will be performed using a MMRM with effects due to baseline FEV₁, sex, age, (pooled) center, previous therapy (ICS or NCS), week, treatment, and week-by-treatment interaction. No explicit structure will be assumed for the covariance among the repeated measures. However, if there is a convergence problem with unstructured covariance, then a compound symmetry covariance structure will be assumed.

The estimated treatment means and treatment mean difference derived from the MMRM analysis between each treatment will be presented together with 2-sided 95% CI for the means and the mean difference with corresponding p-value. An example of the SAS codes is as followed:

```
proc mixed data=fev1cfb;
    class usubjid sex center therapy week trt;
    model cfev=bfev sex age center therapy week trt week*trt
        /ddfm=KR;
    repeated week / type=un sub=usubjid(trt) r;
        ***repeated week / type=cs sub=usubjid(trt) r;
        ***If type=un fails to converge;

    /* Compare active Fp treatment to Placebo over 12 weeks */
    estimate `Fp 25 mcg BID vs Placebo'      trt  1 0 0 -1 /cl;
    estimate `Fp 50 mcg BID vs Placebo'      trt  0 1 0 -1 /cl;

    lsmeans trt week*trt / diff cl;
    ods output Estimates=Est LSMeans=lsmeans Diffs=Diffs;

run;
where: cfev and bfev denote change from baseline and baseline value of
percent predicted FEV1 respectively; week = 1, 2, 3, 4, 5, 6, 7, 8, 9,
10, 11, 12 representing weeks 1 to 12 respectively; and trt is the
treatment for the primary analysis:

    A = Fp MDPI 25 mcg BID
    B = Fp MDPI 50 mcg BID
```

C = FS MDPI 50/12.5 mcg BID
D = Placebo

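### If unstructured covariance fails, compound symmetry with model-based standard errors can misstate the MMRM's week-specific results (SAP 6.4.2.1 and Appendix E)

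*SAP*

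**What the plan says.** SAP 6.3.2.1 to 6.3.2.4 start from unstructured covariance ("No explicit structure will be assumed for the covariance among the repeated measures") and give one fallback ("if there is a convergence problem with unstructured covariance, then a compound symmetry covariance structure will be assumed"). SAP 6.4.2.1, 6.4.2.6 and Appendix E repeat the rule, and Appendices B and C carry it as a code comment. No intermediate structure is named. Protocol 9.5.4.3 names no covariance structure.

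MMRM code appears only in Appendices B, C and E. It requests Kenward-Roger degrees of freedom and no empirical variance option. SAP 6.3.2 and 6.4.2.1 show no MMRM code, so model-based standard errors there are inferred from the appendices.

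The contrasts differ by place:
- SAP 6.3.2: effects over the whole treatment period. For example, the analysis of "PEF over the 12-week treatment period will be performed using an MMRM with effects due to baseline weekly average of daily morning PEF". These endpoints are in the gated sequence of SAP 7.2 ("If the resulting p-value is less than 0.05, the next comparison(s) of interest will be made").
- SAP 6.4.2.1: rescue use "at weeks 4, 8, and 12 will be analyzed using an MMRM". This is an endpoint in the 'other' category, outside that sequence.
- Appendix E: the stated aim is "to estimate the time-averaged difference between treatment groups over 12 weeks", but the code also asks for "lsmeans trt week*trt / diff cl", which gives a difference and interval for each week.
- Appendices B and C: only the treatment main effect, "lsmeans trt / diff cl".

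**The concern.** An unstructured matrix over 12 weeks has 12 × 13 / 2 = 78 covariance parameters. Compound symmetry has two: one variance for every week and one correlation for every pair of weeks. The plan steps from one to the other with nothing between, and a model-based standard error takes the simpler structure as true. Kenward-Roger adjusts for small samples; it does not repair a wrong structure.

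A contrast at a single week would then carry a standard error averaged over weeks. At stake are the confidence intervals and nominal p-values for rescue use at weeks 4, 8 and 12, and the weekly trough FEV₁ differences in Appendix E, which include week 12, the primary time point.

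**Working it through.** **Sample size.** The plan's own figure is reproduced only to fix the setting; it is not disputed. Entering 6.5 and SD 22 (FS versus Fp), then 5 and SD 17 (Fp versus placebo), with 80% power and two-sided 5% (SAP 2.4), n = 2(1.960 + 0.842)²(SD/difference)² gives 180 and 182 per arm, against a stated 181. Then 181/0.88 = 205.7, which rounds up to 206. The standard-error ratios below do not depend on n in large samples.

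**Assumptions.** The documents give no weekly SDs or correlations. The illustration lets the SD of change rise linearly from 10 at week 1 to 17 at week 12. The 17 equals the blinded week-12 trough FEV₁ SD in SAP 2.4; the 10 is assumed. Neither figure describes rescue inhalations.

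**Week-specific contrast, complete data.** Compound symmetry gives every week the mean variance. The ratio of model to true standard error at week t is r = √(mean of SD²)/SD_t, and the actual two-sided error is 2Φ(−1.96 r).

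- *12 weeks fitted.* The 12 variances sum to 2244.9; the mean is 187.1 and its root 13.68. Week 12: r = 13.68/17 = 0.805, error 11.5%. Week 1: r = 13.68/10 = 1.368, error 0.7%.
- *Only weeks 4, 8 and 12 fitted.* The SDs are 11.91, 14.45 and 17; the mean variance is 213.3 and its root 14.60. Week 4: r = 1.226, error 1.6%. Week 8: r = 1.010, error 4.8%. Week 12: r = 0.859, error 9.2%.

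**Other SD paths.** Large-sample comparison of model-based and true variance: two arms of 181, 12 weeks, correlation 0.9 per week and falling with lag. Entries are r and the actual error at week 12.

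| SD, last week / first week | Complete data | 12% dropout |
|---|---|---|
| 1.00 | 1.000, 5.0% | 0.973, 5.7% |
| 1.25 | 0.902, 7.7% | 0.878, 8.5% |
| 1.5 | 0.840, 10.0% | 0.816, 11.0% |
| 2.0 | 0.766, 13.3% | 0.742, 14.6% |
| falling, 1.5 to 1 | 1.260, 1.4% | 1.215, 1.7% |

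**Simulation.** 1,500 null trials per scenario, 206 per arm, 12-25% dropout. With the SD rising from 10 to 17, the week-12 error was 12.5-13.0%; with constant SD 17 it was 5.6-6.4%. With sandwich standard errors every contrast lay between 4.0% and 5.9%.

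**Time-averaged contrast, complete data.** The fitted common variance v and covariance c are the averages of the true variances and covariances. The model variance of the mean over T weeks, (v + (T − 1)c)/T, therefore equals the true one. For the 10-to-17 path with correlation 0.9 per week, v = 187.08 and c = 120.28, so (187.08 + 11 × 120.28)/12 = 125.85. Summing the true covariance matrix and dividing by 144 also gives 125.85. The ratio is exactly 1 and the error 5.0%.

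With 12% dropout the time-averaged ratio is 0.976-1.011 over 12 weeks (error 4.8-5.6%) and 0.971-1.017 for three visits (4.6-5.7%). With 25% dropout the range across both is 0.938-1.036 (4.2-6.6%).

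**The case against.** The strongest reply is that little in the trial depends on this.

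- The fallback sentence sits most prominently in SAP 6.3.2, so a reader might infer that the gated secondary tests there lose type I error control. The documents do not support that. Those contrasts run over the 12 weeks, and their standard error is exact with complete data and within about 3% at the planned 12% dropout.
- A reader might also infer that the week-12 primary results are exposed. They are not: both primary endpoints use ANCOVA with multiple imputation (SAP 6.2.2).
- A third tempting reading is that late-week standard errors will be too small. That holds only if variance rises. With a falling SD the week-12 interval is too wide.
- The error needs unstructured covariance to fail. With about 824 patients that may not happen, and the documents do not say how likely it is. The count of 78 parameters does not apply to C-ACT, which has three post-baseline visits and so 3 × 4 / 2 = 6 parameters. SAP 6.4.2.1 does not say whether 3 or 12 time points are fitted.
- The rule is prespecified, so it leaves no data-driven choice.

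All of this stands. It confines the point to SAP 6.4.2.1, which is outside the testing sequence, and to one output line of a sensitivity analysis. It does not make the fallback a good one for those outputs. The SAP itself foresees non-convergence, and a better fallback can be prespecified just as easily.

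**Conclusion.** The point holds conditionally and is minor. If unstructured covariance fails and the variance of change differs across weeks, the week-specific intervals in SAP 6.4.2.1 and Appendix E can be wrong in either direction. Under the assumed rise in SD from 10 to 17, the week-12 type I error is about 9% in a three-visit model and 11-13% in a 12-week model. With equal variances it is 5-6%, and with a falling SD the test is conservative. These sizes rest on assumed SD paths and correlations, and on the inference that the models without displayed code also use model-based standard errors. The conclusions that control the trial's success do not change.

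**What to change.** In SAP 6.4.2.1 and Appendix E, replace the fallback with a fixed order: unstructured, then heterogeneous Toeplitz, then heterogeneous AR(1), then compound symmetry, taking the first that converges. State that any structure other than unstructured uses the empirical (sandwich) variance. Over 12 weeks the two intermediate structures need 12 + 11 = 23 and 12 + 1 = 13 parameters, and both let the variance differ by week. State also whether SAP 6.4.2.1 fits 3 or 12 time points. The same sentence can go into 6.3.2.1-6.3.2.4, 6.4.2.6 and Appendices B and C for consistency only.

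The cost is one sentence per section, in a SAP amendment before database lock; Protocol 9.5.4.3 needs no change. Kenward-Roger degrees of freedom are not available with the sandwich estimator, which is immaterial at about 200 patients per arm.

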9.5.4.3. Secondary Efficacy Analysis

For all secondary endpoints, analyses will be performed using the ITT analysis set and will not include retrieved dropout data in the analysis.

Analysis of change from baseline in weekly average of daily trough morning PEF, total daily use of albuterol/salbutamol, total daily asthma symptom score, and C-ACT score over the 12-week treatment period will be analyzed using an MMRM analysis with effects due to baseline, sex, age, (pooled) investigational center, previous therapy (ICS or NCS), treatment, time, and time-by-treatment interaction. For all of these endpoints, the MMRM will use only observations collected until IMP discontinuation.

The time to first onset of effect, defined as the first decrease from baseline in daily rescue medication use, will be analyzed using a log-rank test. Median and mean time to first onset of effect and associated 95% CIs will be estimated. Time to first onset of effect will also be displayed graphically with a Kaplan-Meier figure.

The proportion of patients who discontinued from IMP for asthma exacerbation during the 12-week treatment period will be analyzed using a logistic regression model with effects due to previous therapy (ICS or NCS) and treatment. These patients will be considered as nonresponders in this analysis.

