2.2. Randomization and Blinding

This is a double-blind, parallel-group, placebo-controlled, randomized clinical study. Patients who meet all randomization criteria at the RV will be stratified by previous therapy (ICS or NCS) and randomly assigned into a 1:1:1:1 ratio to receive Fp MDPI 25 mcg, Fp MDPI 50 mcg, FS MDPI 50/12.5 mcg, or placebo MDPI, twice daily, for the entire treatment period. Randomization will be assigned via IRT. Patients being treated with a combination of ICS/NCS will be stratified as an ICS patient.

Approximately 206 patients will be randomized into each treatment group (approximately 824 patients in total). After the run-in period, patients and parents/legal guardians/caregivers will remain blinded to randomized treatment assignment during the study. In addition, the investigator and the sponsor's clinical personnel involved in the study will be blinded to the IMP identity after the run-in period until the database is locked for analysis and the treatment assignment is revealed.

No effort will be made to maintain a balance among treatment groups within an investigational center.

Patients will be randomly assigned to treatment groups by means of a computer-generated randomization list. The specifications for randomization will be under the responsibility and oversight of Teva Global Statistics. The output of the randomization process will be a patient randomization list.

The sponsor's clinical personnel involved in the study will be blinded to the identity of the treatment until the database is locked for analysis and the treatment assignment revealed.

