6.4.2.10. Time to Consistent Onset of Effect in Daily Rescue Medication Use

The time to consistent onset of effect is defined as the number of days elapsed from the date of randomization to the first date of 3 consecutive days with a decrease from baseline in daily rescue medication use. Patients who have 3 consecutive days with a decrease in effect will be counted as an event in the analysis, otherwise, patients will be right-censored at the date of last IMPDV assessments.

The analysis of time to consistent onset of effect will be performed using a log-rank test to compare the survival curves. Time to first onset of effect will be graphically displayed with a Kaplan-Meier figure and the median time to first onset and associated 95% CIs will be provided.

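### The log-rank and Wilcoxon tests leave out the ICS/NCS randomization stratum: they stay valid, but stratifying them is a free improvement if previous therapy is prognostic

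*SAP*

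**What the plan says.** SAP 2.2 has one stratification factor: patients "will be stratified by previous therapy (ICS or NCS") and are "randomly assigned into a 1:1:1:1 ratio to receive Fp MDPI 25 mcg" or one of the other three arms.

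That factor is carried into most comparative analyses:
- the primary ANCOVAs (SAP 6.2.2.1 and 6.2.2.2) and the week 1 ANCOVA (6.4.2.5);
- the MMRMs (6.3.2.1 to 6.3.2.4, 6.4.2.1, 6.4.2.6, Appendix E);
- the logistic models (6.3.2.6, 6.4.2.8), and the CMH fallback in 6.3.2.6, which is itself stratified by previous therapy.

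It is absent from five:
- Time to first onset (SAP 6.3.2.5), whose analysis "will be performed using a log-rank test to compare the survival curves". Protocol 9.5.4.3 likewise says only that it "will be analyzed using a log-rank test".
- Time to consistent onset (SAP 6.4.2.10): "The analysis of time to consistent onset of effect will be performed using a log-rank test to" compare the curves.
- Rescue-free, symptom-free and asthma-control days (SAP 6.4.2.2 to 6.4.2.4), each "compared between treatment groups using the Wilcoxon-Mann-Whitney test".

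The example code agrees with the text. PROC LIFETEST has `strata treat;`, which names the groups being compared and adjusts for nothing. PROC NPAR1WAY has `class treat;` only. No reason is given for the difference from the other analyses.

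**The concern.** When arms are balanced within a prognostic stratum by design, an unstratified rank test leaves the between-stratum variation in its reference distribution, although the design has largely removed that variation from the treatment comparison. For the log-rank test, pooling strata with different hazards also pulls the treatment effect toward the null. The result is lost power and, if the stratum is strong enough, a test that rejects less often than its nominal level.

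Time to first onset is endpoint [E] in the sequences of SAP Tables 8 and 9, with two comparisons in the first and three in the second. Under SAP 7.2, a p-value above 0.05 stops further testing of that strength and of that measure. A miss on [E] therefore also closes [F] for that comparison and the remaining [E] comparisons to its right. The other four endpoints are outside the sequence.

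**Working it through.** **The plan's own figure.** The only sizing is for the primary endpoints. Reading the stated 6.5% and 5% as treatment differences, n per arm = 2 × (1.960 + 0.842)² × (SD/difference)². This gives 15.70 × (22/6.5)² ≈ 180 and 15.70 × (17/5)² ≈ 182 (180.8 and 182.4 with the t distribution), against the stated 181. Then 181/(1 − 0.12) = 206: "Approximately 206 patients will be randomized into each treatment group". No power, hazard ratio or event count is stated for any log-rank or Wilcoxon endpoint.

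**Inputs.** From the documents: 206 per arm, 1:1 in each pair, two strata, two-sided 0.05, about 84 days of follow-up. Assumed, because the documents do not give them: stratum split, stratum effect, treatment effect, event rate, and permuted blocks of 4 within strata.

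**Log-rank, exponential times to onset** (4,000 runs per cell; treatment HR 1.33 at a daily hazard of 0.3, or 1.37 at 0.02). As an anchor with no stratum effect, at hazard 0.3 all 412 patients have events, so z = ln(1.33) × √(412/4) = 0.285 × 10.15 = 2.89 and power = Φ(2.89 − 1.96) ≈ 82%. The simulation gives 82.5%.

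Each cell shows power unstratified / stratified, in percent:

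| Stratum HR | 50:50, hazard 0.3 | 50:50, hazard 0.02 | 70:30, hazard 0.3 | 70:30, hazard 0.02 | Gain, points |
|---|---|---|---|---|---|
| 1 | 82.5 / 82.3 | 85.1 / 85.1 | 80.8 / 80.7 | 85.0 / 84.5 | about 0 |
| 1.5 | 78.9 / 80.6 | 83.4 / 84.9 | 80.0 / 81.1 | 81.8 / 83.1 | 1–2 |
| 2 | 75.1 / 81.3 | 78.2 / 83.0 | 77.0 / 80.8 | 78.0 / 81.4 | 3–6 |
| 3 | 66.9 / 81.0 | 69.3 / 82.8 | 71.9 / 80.7 | 69.4 / 79.6 | 9–14 |

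Under the null, the unstratified test had size 3.5% to 4.7% at a stratum HR of 2 and 2.8% to 3.8% at 3. The stratified test ran at 4.5% to 6.0% throughout. The Monte Carlo standard error is about 0.3 points for size and 0.5 to 0.7 for power. A separate exponential set with stratum HRs of 0.6, 0.4 and 0.25 gave unstratified power of 75%, 68% and 56% against about 79% stratified, with unstratified size 4.3%, 3.3% and 2.0%.

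**Log-rank under the SAP's own onset rule.** SAP 6.3.1.5 defines the event against the patient's own baseline. Simulating that rule (gamma-Poisson daily inhalations, 7-day baseline, event on the first day below it, 206 per arm, 60/40 strata, 25% treatment reduction, 1,500 runs) gave:
- strata differing 1.5- or 2-fold in rescue use: stratum HR only 1.04 to 1.06, gain 2 to 3 points (38% to 40%, 48% to 51%);
- 3-fold: 6 points;
- 4-fold (mean 0.5 against 2 inhalations a day): 10 points, and about 11 in a repeat simulation;
- size of the unstratified test: 4% to 6%, so no visible conservatism.

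**Wilcoxon against van Elteren** (normal outcome, treatment shift 0.28 SD, 6,000 runs per cell; 50:50 then 70:30 strata):

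| Stratum shift | Power unstratified / stratified, % | Size, unstratified, % |
|---|---|---|
| 0 | 79.6 / 79.5; 79.2 / 78.9 | 4.7; 5.2 |
| 0.25 SD | 78.2 / 78.6; 79.6 / 79.7 | 4.8; 5.4 |
| 0.5 SD | 77.1 / 79.0; 76.6 / 77.8 | 3.9; 4.0 |
| 1 SD | 71.5 / 79.1; 72.2 / 78.5 | 2.6; 3.7 |

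**The case against.** The strongest reply is that nothing here is an error. Unstratified log-rank and Wilcoxon tests are valid under stratified randomization, and the SAP implements the test that the protocol names. All of that stands. A reader might infer from the omission that these p-values are invalid or anti-conservative. The documents do not support that: any departure is toward too few rejections.

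A reader might also infer a large loss of power and a test that runs well below 5%. That needs a strong stratum effect, and the documents give no split, event rate or prognostic strength from which to argue one. The endpoint itself points the other way. Both strata stop their nonstudy asthma drugs, take placebo through run-in and meet the same C-ACT and FEV₁ criteria, and onset is judged against the patient's own baseline. Under that rule the gain was 2 to 3 points for realistic-looking differences, and the conservatism did not appear. For the Wilcoxon endpoints, a gain of 6 to 8 points needs a full 1-SD shift between strata in a change-from-baseline variable.

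The consequence is also limited. [E] is reached only after all three primary tests and the earlier secondary endpoints on its path succeed, and SAP 7.2 itself says the secondary procedure does not control overall type I error and reports nominal p-values.

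What does not stand is the inference that the change is therefore not worth making. Stratifying cost at most about half a point of power where the stratum did nothing, and the sponsor chose this factor for randomization and adjusts for it in its model-based tests.

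**Conclusion.** The omission is confirmed in text and code, and it is a matter of efficiency, not validity. Stratifying gains about nothing if previous therapy is not prognostic. It gains roughly 2 to 6 points of power for moderate effects (stratum HR near 2, or a 1.5- to 2-fold difference in rescue use), slightly less at a stratum HR of 1.5, and about 10 points or more only for strong effects. Conservatism, with size about 2% to 4%, appears under strong stratum hazard ratios but not under the self-referenced onset rule. All of these sizes rest on assumed stratum splits, stratum effects, treatment effects and event rates, and on a randomization list that balances arms within strata. One endpoint in the secondary sequence and four outside it are affected. The primary analyses are not. This is a free improvement.

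**What to change.** Before unblinding, by SAP amendment as SAP 2.5.2 allows:
- Both onset endpoints: a log-rank test stratified by previous therapy, `strata therapy / group=treat;` in PROC LIFETEST, using the stratum under which the patient was randomized.
- Rescue-free, symptom-free and asthma-control days: a van Elteren test stratified by previous therapy, for example PROC FREQ with `tables therapy*treat*change / cmh scores=modridit;`.
- Keep the existing call with `strata treat;` for the Kaplan-Meier curves and medians by treatment, and note under the figure that the p-value is stratified.
- Record the change in SAP Section 11. Time to first onset needs the entry because Protocol 9.5.4.3 names an unqualified log-rank test. Protocol 9.5.4.4 leaves the methods for the other four endpoints to the SAP.

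The cost is a few lines of code, text edits in SAP 6.3.2.5, 6.4.2.2 to 6.4.2.4 and 6.4.2.10, and one table entry. No sample size or data collection changes. Made after unblinding, the same switch would look data-driven.
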